Procedural protocol: Patient randomization will be stratified by site and performed through the RedCap database system which will be available within the procedure room. Equal allocation to 1 of 2 exposure groups will be performed: PRP and SAI. At procedure start 20 mL of blood will be drawn from the patient (no matter which group they are randomized to in order to maintain consistency between procedure types). Following this, a clinical nurse will administer the PROs and functional assessments and then exit the room. The research coordinator will perform the randomization through RedCap, and the assigned injectate (PRP or SAI) will be drawn by the physician and injected into the patient (who is blinded to the injectate type).

- PRP therapy: The SIJ will be localized under CT fluoroscopy. Local lidocaine anesthetic will be provided at the entry site. A 22-gauge Quincke needle will be advanced into the SIJ under CT fluoroscopic guidance. After autologous whole blood centrifugation with the Cascade Autologous Platelet System each sample will be evaluated with a platelet counter to assess integrity of the PRP injectate and specify leukocyte rich vs. poor preparation. Autologous platelet-rich plasma (generally 3-5 cc yield after centrifugation) will be injected into the SIJ after activation with calcium chloride.
- SAI therapy: The SIJ will be localized under CT fluoroscopy. Local lidocaine anesthetic will be injected at the entry site. A 22-gauge Quincke needle will be advanced into the SIJ under CT fluoroscopic guidance. 40 mg depomedrol mixed with 2 mL of 0.25% bupivacaine will then be injected in the SIJ (total of 3 mL).

Approximately 30 minutes following, the clinical nurse blinded to group allocation will re-enter the room and again perform patient assessments. The patient will then be given general post-injection instructions, be asked their preferred method of contact, and be discharged. The patient will remain blinded to the procedure arm throughout the study. A blinded research assistant will remotely contact the patient to obtain NRS and opiate measures at 3 and 7 days, and 2 months post-procedure. A blinded clinical nurse will perform in-person functional and disability assessments and obtain NRS and opiate measures at 1 and 3 months post-procedure.

Primary Aim

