responder analysis⁵⁷ will also be performed with at least a 2-point reduction in NRS at 3 months compared to baseline used as the endpoint, with a separate analysis performed on those who improved by 50%. Responder analyses will also be performed on MODQ and SF-12 results that meet the minimally important clinical change.^{58,59} Comparison of proportions will be performed with Fishers' exact test.

Tertiary/Exploratory Aim

Design: This will be an exploratory study to investigate MR imaging biomarkers in SIJ pain and determine whether there are changes in cartilage or periarticular signal with PRP and SAI therapy between baseline and 6 months. Additionally, differences in cartilage or periarticular signal between symptomatic and asymptomatic joint pain within the same individual will be investigated in both baseline and 6 months studies.

Inclusion criteria: Unilateral SIJ pain and all additional criteria from primary aim. This will allow comparison to baseline scan as well as comparison to an asymptomatic joint within the same patient.

Exclusion criteria: MRI contraindications per ACR guidelines and all additional criteria from primary aim.⁶⁰

Sample Size: 5 subjects will be recruited from each exposure group (PRP and SAI) for imaging analysis (10 patients total).

Acquired Clinical Data: See primary and secondary aims.

Advanced MR Imaging Parameters: MRI will be obtained pre-procedure as a baseline (at least one week after diagnostic block to ensure resolution of procedural changes), then again 6 months after SAI or PRP to measure T1 and T2 maps, as well as perfusion/diffusion properties.^{24,40}

The following sequences will be obtained with the following parameters:

T2 mapping: TR = 500 ms, ETL = 9, TE = 15, 30, 45, 60, 75 msec; bandwidth = 500 Hz/pixel; spatial resolution 1x1x3 mm³; acquisition matrix = 256x84x32

T1 rho: 3D FLASH: slice thickness 3 mm, FOV = 256 mm, resolution = 1x1x3 mm³; averages = 2, imaging; matrix = 256x256x16, 25% slice oversampling; 12 shots per each spin-lock duration; TR/TE = 6/3 ms, group TR = 4000 ms; bandwidth/pixel = 560 Hz/pixel; spin-lock durations : 0, 10, 20, 30, 40, 50 ms; B1 field: 500 Hz (1.18 Gauss); acquisition time = 8:00 min

IVIM: DWI in 3 planes (resolution = 1.8 x 1.8 x 3.3 mm) using the following b-values: 0, 10, 20, 30, 50, 80, 100, 200, 400, and 800 s/mm².⁴⁷ A STIR sequence will also be performed to evaluate periarticular inflammation.⁶¹

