Post-Processing: Using a home developed processing software, which was developed using Python 3.x programming language, T2 and T1Rho maps are constructed by pixel-by-pixel fitting of the measured T2-weighted images and T1Rho source images to a function "single-exponential + constant" with respect to the echo-times (TE) and spin-lock durations, respectively. Osirix will be used for IVIM post-processing and region of interest (ROI) analysis.

Outcomes and their measurements: T1rho: cartilage relaxation time calculated in msec. T2 mapping: cartilage T2 intensity measured in regions of interest. IVIM: Perfusion parameters calculated by f (perfusion fraction), D* (pseudodiffusion), and fD*. Diffusion parameters calculated by D (tissue diffusion).

Analyses: The investigators will compare the two groups with respect to a mean difference in T1rho relaxation time from baseline to 3 months using a two-sample t-test as the investigators tertiary endpoint analyses. This method of analysis will also be performed for T2 mapping intensity, as well as IVIM parameters as stated above. The investigators will provide 95% confidence intervals to indicate the uncertainty in these estimates. The investigators will compare the mean parameters of the symptomatic joint to the contralateral asymptomatic joint within the same subject using a paired t-test and provide 95% confidence intervals to indicate the uncertainty in these estimates.

References

2. From the Centers for Disease Control and Prevention. Prevalence of disabilities and associated health conditions among adults--United States, 1999. *JAMA : the journal of the American Medical Association*. 2001;285(12):1571-1572.

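### Does planning 5 imaging patients per arm and 10 in total conflict with scanning them before they are randomised?

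*Combined protocol and SAP*

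**What the plan says.** The Sample Size paragraph of the Tertiary/Exploratory Aim states that "5 subjects will be recruited from each exposure group (PRP and SAI) for imaging analysis (10 patients total"). It gives no effect size, standard deviation or power. Eligibility is "Unilateral SIJ pain and all additional criteria from primary aim", plus freedom from MRI contraindications.

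On timing, Advanced MR Imaging Parameters says that "MRI will be obtained pre-procedure as a baseline (at least one week after diagnostic block to ensure resolution of procedural changes"), with a second scan at 6 months.

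The Procedural protocol puts randomisation on the procedure day. Blood is drawn first. Then: "Following this, a clinical nurse will administer the PROs and functional assessments and then exit the room". Only after that: "The research coordinator will perform the randomization through RedCap, and the assigned injectate (PRP or SAI) will be drawn by the physician". On the method it says "Patient randomization will be stratified by site and performed through the RedCap database system which will be available within the procedure room", with equal allocation to the two arms. Imaging participation is not a stratum.

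The imaging Analyses paragraph plans a two-sample t-test between arms and a within-patient comparison: "The investigators will compare the mean parameters of the symptomatic joint to the contralateral asymptomatic joint within the same subject using a paired t-test".

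**The concern.** The wording suggests drawing five patients out of each treatment group, yet no group exists when the patient is recruited and scanned. Site is the only stratum, so nothing holds the imaging subset to an equal split. If exactly ten are scanned, 5:5 is a matter of chance. If exactly five per arm are wanted, the number of baseline scans becomes random and someone who can see allocations must keep count. The text does not say which figure gives way.

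At stake would be the precision of the between-arm imaging comparison, the number of scans to budget for, and an unplanned decision partway through if the split came out uneven.

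**Working it through.** **Inputs from the protocol.** 5 per arm and 10 in total (imaging Sample Size); 1:1 allocation stratified by site (Procedural protocol); 25 per arm and 50 in total (main Sample Size). Block size, imaging uptake and the split between sites are not given, so anything that depends on them is an assumption.

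**1. The plan's own figure.** 2 × 5 = 10. It reproduces exactly. There is no imaging power calculation to check.

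**2. Chance of each split if ten are scanned before allocation.**

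Simple allocation: P(k in one arm) = C(10,k)/2^10. For example, P(5:5) = 252/1024 = 0.246. Random ten from a list balanced at 25:25: P(k) = C(25,k)·C(25,10−k)/C(50,10).

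| Split | Simple | From 25:25 |
|---|---|---|
| 5:5 | 24.6% | 27.5% |
| 6:4 | 41.0% | 43.6% |
| 7:3 | 23.4% | 21.5% |
| 8:2 or worse | 10.9% | 7.4% |

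Simulated permuted blocks within site (assumed blocks of 2 to 10, uptake 30% to 100%, two site mixes) give 5:5 in 28% to 75% of trials and 7:3 or worse in 0% to 27%. So 5:5 is never assured.

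**3. What an uneven split costs.** With a common SD, the standard error relative to 5:5 is √[(1/a + 1/b)/(2/5)]. The detectable difference uses the noncentral t with 8 df, two-sided 5%, 80% power. The 95% CI half-width is 2.306·√(1/a + 1/b).

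| Split | SE ratio | Detectable difference | CI half-width |
|---|---|---|---|
| 5:5 | 1.00 | 2.02 SD | 1.46 SD |
| 6:4 | 1.02 | 2.07 SD | 1.49 SD |
| 7:3 | 1.09 | 2.21 SD | 1.59 SD |
| 8:2 | 1.25 | 2.53 SD | 1.82 SD |

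Even a perfect split detects only a difference of about 2 SD. Forcing 5:5 would not turn the comparison into a confirmatory one.

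**4. The main trial uses the same form.** The main Sample Size paragraph plans 25 per arm and 50 in total, again for patients enrolled before allocation. Under simple randomisation 50 patients split exactly 25:25 with probability C(50,25)/2^50 = 0.112. Nobody would call that plan contradictory, because a per-arm number under 1:1 allocation is an expectation. The imaging sentence deserves the same reading.

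**5. Is a second reading really open?** The alternative is to keep scanning until each arm has five. Under simple allocation that needs 12.5 scans on average, and 16 or fewer in 92.3% of trials. It requires separating patients scanned from patients analysed, which the text never does. The sentence governs how many are recruited and closes with a total of ten, so 12 to 16 scans would depart from it.

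**The case for a change.** The strongest case for raising the point is that the order of events is explicit, the probabilities are right, and an uneven split is likely under most assumptions. The total of ten is attached to imaging analysis, so it does not beyond doubt cap baseline scans. One sentence would spare the team a decision partway through. The facts in this stand. What they support is an optional clarification: an expected size is stated, and the realised split will vary around it.

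A more technical objection has some force. It is tempting to say that the t-test is valid whatever the split, but the pooled t-test needs equal variances when arms are unequal, and the plan specifies neither that nor a Welch test. Assume an SD ratio of 2. By simulation, the pooled test at 7:3 has a type I error of about 13.7% when the smaller arm is the more variable and 1.9% when it is the less variable. At 5:5 it is about 5.8%. So imbalance is not wholly harmless. This sensitivity depends on an assumed variance ratio and on the choice of test, and it would not be cured by stating whether five per arm or ten in total governs. The paired comparison of the two joints within a patient does not depend on arm balance.

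**Conclusion.** The concern does not hold. The two figures agree and describe a planned size under equal allocation, in the form the protocol uses for the main trial. Following the plan as written gives ten scanned patients and a split that is often uneven: 6:4 or worse in 75.4% of trials under simple allocation (100% − 24.6%). With a common SD, the standard error rises by 2% at 6:4, 9% at 7:3 and 25% at 8:2. The comparison is labelled exploratory, has no power claim, and detects only about 2 SD at best.

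The split probabilities rest on the assumed allocation method, since block size and imaging uptake are not stated, and all counts are before any loss by 6 months. Under any of these assumptions the conclusion is the same: what remains is a choice of wording.

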Tertiary/Exploratory Aim: To compare mean intraarticular and periarticular MRI parameters (T1 relaxation time/T2 intensity and periarticular diffusion and perfusion) signal changes in chronic SIJ dysfunction with PRP vs. SAI therapy at 6 months.

Hypothesis: PRP will demonstrate superior pain control and disability outcomes compared to SAI at 3 months, and potentially result in intraarticular chondroprotection and/or anti-inflammatory periarticular changes that will be quantifiable using advanced MRI techniques.

Background and Significance

Prevalence and costliness of low back pain

Low back pain (LBP) is one of the most common causes of US workforce disability, and due to its effect on productivity and resultant lost wages, one of the costliest conditions to manage.¹⁻⁴ It is estimated to affect up to two thirds of people in their lifetime and is only increasing in prevalence (up to 170%).^{1,5} Likewise, therapies for chronic LBP including opioid use, spinal injections, and surgery have also increased in the last two decades, with opioids the most commonly prescribed medication, used long-term in nearly 76% of cases.⁶⁻⁹ Because of increasing incidence and recurrence, LBP makes up a substantial amount of the rising healthcare costs over the past two decades, exceeding over \$100 billion per year.^{1,10} Additionally, long-term opiate usage in LBP has substantially contributed to the opioid crisis.⁹ This has led to a translational research initiative from the National Institute of Health (NIH Back Pain Consortium [BACPAC] Research Program) to develop more effective therapies for this prevalent and debilitating condition.¹¹

Sacroiliac joint pain

The sacroiliac joint is (SIJ) thought to be the pain generator in up to 30% of cases of LBP.⁵ Chronic pain can be separated into mechanical sacroiliitis (joint instability with or without periarticular inflammation) and non-mechanical etiologies (spondyloarthropathies). Instability is related to the angle of the weight-bearing joint, possibly contributing to the slight increased prevalence in females who have a more horizontal joint surface¹², as well as with dysfunction of the regional stabilizing ligaments (iliosacral, iliolumbar, sacrotuberous, sacrospinal ligaments).¹³ Pain localization is performed by a combination of history, imaging, physical examination, and diagnostic block.¹³ Multi-test physical maneuvers have shown to be promising for localization

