Outcomes and their measurements: The primary outcome of pain will be assessed using NRS which will be recorded pre and immediately post treatment in person, at 3 days, 1 week and at 1, 2, and 3 months post-procedure.

Analyses: The investigators will compare the two groups with respect to a mean difference in NRS from baseline to 3 months using a two-sample t-test as the investigators primary endpoint analysis. The investigators will provide 95% confidence intervals to indicate the uncertainty in these estimates. Additional analyses will evaluate the mean difference at 3 days, 1 week, 1 and 2-months post-treatment. A subanalysis will also be performed in subjects who had 80% relief by diagnostic block to determine the effect of the diagnostic cutoff.

Secondary Aim

Outcomes and their measures: The secondary outcomes of disability and quality of life will be analyzed using the Modified Oswestry Disability Questionnaire (MODQ)⁵², Short Form 12 (SF-12) Health Survey⁵³ scores, and opiate usage (by Morphine Equivalent Dose) as reported by the patient and chart review.

Functional outcomes will be analyzed by the following two tests which have been previously validated to assess physical status⁵⁴:

- The “get-up and go test”⁵⁵: The time (in seconds) that it takes a patient to rise from a chair, walk three meters, turn around, walk back to the chair, and sit down is measured.
- The “5 time sit to stand test”⁵⁶: The time (in seconds) it takes the patient to rise from sitting to standing 5 times is measured.

Disability and functional assessments will be performed in-person pre-procedure, immediately post-procedure, as well as 1 and 3 months post procedure. Additionally, reported opiate usage will be assessed at the same time periods as NRS as in the primary aim.

Analyses: The investigators will compare the two groups with respect to a mean difference in survey (SF-12, MODQ) scores from baseline to 3 months using a two-sample t-test as the investigators secondary endpoint analyses. This will also be done to assess the results of the physical functional tests, as well as reported opiate usage. The investigators will provide 95% confidence intervals to indicate the uncertainty in these estimates. A

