1. Administrative Changes: this includes adding a new investigator and correcting previous typos, grammatical errors, and other mistakes/omissions.

2. Changes to study design:

a. The investigators are removing the inclusion criteria of ["In patients with severe pain (>/=8 by NRS) where the effect of lidocaine may be more limited, a clinically meaningful reduction in NRS (at least 2 points) will also qualify for the study"] that was previously added via amendment to the study.

b. The investigators are changing the enrollment goal back to 50.

3. Changes to study procedures:

a. The investigators are removing the two week cross-over arm that was previously added via amendment to the study.

b. The investigators are removing the changes made to the statistical analysis portion that were made following the additions of the two week cross-over arm and the extra pain inclusion criteria.

4. Changes to consent documents - the changes to the consent forms will reflect the above changes listed.

Describe the reason for each of the changes described above. List and number the reasons according to the list above.

1. Administrative Changes – the investigators are adding a study coordinator to the team, and correcting previous typos, grammatical errors, and other mistakes/omissions.

2. Changes to study design:

a. The study team has decided that the addition of the extra pain inclusion criteria was unnecessary.

b. The enrollment goal was changed to 60 following the addition of the two week cross-over arm, to account for the statistical analysis changes that were also made. The cross-over arm is being removed, so the enrollment goal is being changed back to the original goal of 50.

3. Changes to study procedures:

a. The study team has decided that the addition of the cross-over arm was unnecessary and will only delay the trial. Subjects who choose to end the trial and receive a different treatment for their SI pain will be marked as treatment failures.

b. Changes were made to the statistical analysis procedures to account for the additions of the two week cross-over arm and additional pain inclusion criteria to the study. Since the investigators are removing both those previous changes, the investigators are thus removing the corresponding statistical analysis changes.

4. Changes to consent documents: the changes to the consent documents will reflect the above changes.

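### No pain score or record of further SIJ treatment is scheduled after 3 months, although the outcome MRI is at 6 months

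*Combined protocol and SAP*

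**What the plan says.** All references are to the combined protocol and SAP.

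- **Pain.** Primary Aim, outcomes: NRS is taken before and immediately after treatment, then "at 3 days, 1 week and at 1, 2, and 3 months post-procedure".
- **Last contact.** Procedural protocol: "A blinded clinical nurse will perform in-person functional and disability assessments and obtain NRS and opiate measures at 1 and 3 months post-procedure". The remote contacts fall at 3 days, 7 days and 2 months.
- **Opiate use.** Secondary Aim: "reported opiate usage will be assessed at the same time periods as NRS as in the primary aim", so it also ends at 3 months.
- **Disability and function.** Secondary Aim: before and immediately after the procedure, "as well as 1 and 3 months post procedure".
- **Imaging.** The statement of the tertiary aim concerns "signal changes in chronic SIJ dysfunction with PRP vs. SAI therapy at 6 months". Under Advanced MR Imaging Parameters, the second scan is taken "then again 6 months after SAI or PRP to measure T1 and T2 maps".
- **Purpose of the imaging.** Tertiary/Exploratory Aim, Design: "This will be an exploratory study to investigate MR imaging biomarkers in SIJ pain". The same paragraph plans a comparison of the symptomatic with the asymptomatic joint in the same patient, at baseline and again at 6 months.
- **Clinical data for the imaging aim.** None of its own; the text refers back to the primary and secondary aims.
- **Other treatment.** The Amendment 3 rationale says: "Subjects who choose to end the trial and receive a different treatment for their SI pain will be marked as treatment failures".
- **Imaging analysis.** The Analyses paragraph of the tertiary aim gives the between-arm T1rho comparison as baseline to 3 months, which disagrees with the 6-month scan.

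**The concern.** The imaging aim is about markers of SIJ pain, but at its only post-treatment scan nobody is scheduled to ask whether the joint hurts. Two planned analyses are affected.

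The first is the within-patient joint comparison at 6 months. Patients enter this subset with unilateral pain, so at baseline one side is known to be painful and the other not. Six months after treatment the treated side may be painless, or the other side may have become painful. The paired test would still use the baseline labels.

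The second is the between-arm comparison of MRI change. An SIJ procedure after the 3-month visit could itself alter the measured signal. The plan allows for this at the start: the baseline scan must follow the diagnostic block by at least a week so that procedural changes resolve, and SIJ steroid in the preceding 6 months excludes entry. There is no corresponding record before the outcome scan.

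**Working it through.** **Schedule side by side**

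| Item | Last scheduled time | Section |
|---|---|---|
| NRS | 3 months | Primary Aim, outcomes |
| Opiate use | 3 months | Secondary Aim |
| Disability, function | 3 months | Secondary Aim |
| Patient contact other than MRI | 3 months | Procedural protocol |
| Record of further SIJ treatment | none scheduled | – |
| Outcome MRI | 6 months | Tertiary aim; MR Imaging Parameters |
| MRI analysis (T1rho) | 3 months | Tertiary aim, Analyses |

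The gap is 6 − 3 = 3 months. It follows from the 6-month scan, which is stated in the aim, in the design paragraph and in the imaging section. Only the Analyses paragraph says 3 months. If the scan were at 3 months, most of the gap would close.

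**The plan's own figures.** The only stated power is for the main trial. With 20 per arm, 80% power and two-sided 5%, the noncentral t gives a detectable standardised difference of 0.909. Multiplying by SD 2, 2.5 and 3 gives 1.82, 2.27 and 2.73, against the stated 1.8, 2.3 and 2.7. Allowing for dropout, 20/(1 − 0.20) = 25 per arm. These figures reproduce, and this point changes none of them.

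**Chance that an interim procedure matters.** The documents give no rate of further SIJ procedures, so the risk p per patient before the scan is assumed. The chance of at least one among 10 is 1 − (1 − p)^10:

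- p = 4%: 1 − 0.96^10 = 34%
- p = 10%: 1 − 0.90^10 = 65%
- p = 20%: 1 − 0.80^10 = 89%
- p = 30%: 1 − 0.70^10 = 97%

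The low value is in line with the service's count in the Sample Size section of 54 SAI on 52 individuals in 12 months (2 repeats / 52 = 3.8%). That count is not an estimate for trial patients.

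**Scale in a subset this small.** One patient is 1/5 = 20% of an arm. At 5 per arm, 80% power and two-sided 5%, the detectable difference is 2.02 SD. Leaving out one re-treated patient (4 v 5) makes it 2.19 SD; leaving out one per arm (4 v 4) makes it 2.38 SD. Exclusion therefore has a price and should not be the main analysis.

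**The case against.** **No imaging–pain correlation is planned.** A reader might infer that imaging change cannot be related to pain at all. The documents do not support that. NRS is available before treatment and at 3 months, so MRI change could be set against 3-month pain. The baseline half of the joint comparison is intact, because the unilateral-pain criterion fixes the painful side. What is missing is pain at the time of the second scan.

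**The Amendment 3 sentence concerns patients who leave.** It might be read as evidence that the plan expects scanned patients to have other injections without a record. It covers subjects who end the trial, and they are marked as treatment failures. It does show that other SIJ treatment was foreseen. It does not say how or until when such treatment is ascertained, or whether those patients are scanned and analysed for MRI.

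**Dilution.** It is tempting to say that one re-treated patient cuts the contrast by 20%, raising the detectable difference to 2.02/0.8 = 2.53 SD. That holds only if the patient takes on the full effect of the other arm. A repeat of the same injectate, or both treatments in sequence, need not act that way.

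**Chart review.** The plan already uses charts for medication data, so some later procedures might be found in retrospect. None is scheduled for this purpose, and pain at the scan could not be reliably recovered that way.

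**Exploratory aim.** Ten patients and no claimed power mean that no main conclusion depends on this. That stands, and it limits the weight of the point. It is not a reason to omit a few questions.

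**Conclusion.** The point holds as a cheap improvement to the exploratory imaging aim. The clinical schedule ends 3 months before the outcome scan. The 6-month joint comparison therefore lacks current symptom status, and the between-arm MRI comparison is open to interim procedures that nobody is scheduled to record. How often they would occur is unknown; the 34% to 97% range rests on assumed risks of 4% to 30%. The conclusion also rests on 6 months being the intended scan time, and on the text available for review, in which a short part of the imaging background was not included. The primary endpoint, the main sample size and the baseline joint comparison are unaffected.

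**What to change.** 1. At the 6-month MRI visit of the 10 imaging patients, record NRS for each side, opiate use, and any SIJ injection or procedure since the last contact.
2. Use symptom status at 6 months to interpret the 6-month joint comparison. Report MRI change alongside NRS change over the same 6 months descriptively only: by the Fisher z approximation, 10 patients give 80% power only for a correlation near tanh((1.96 + 0.84)/√7) = 0.79.
3. Keep the between-arm MRI comparison as randomised in all scanned patients. List those with an interim procedure, and show the comparison without them only as a sensitivity analysis, since it excludes on an event after randomisation that is probably related to response.
4. State whether patients marked as treatment failures are scanned and how their scans are analysed.
5. Reconcile the 3-month time point in the tertiary Analyses paragraph with the 6-month scan stated elsewhere.

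The cost is a few questions for 10 patients at a visit they already attend, one extra table and a short text correction. Treatment, sample size and the primary analysis do not change.

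### The between-arm imaging analysis tests change to 3 months, but MRI is scheduled only at baseline and 6 months, so the test as written has no data

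*Combined protocol and SAP*

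**What the plan says.** The combined protocol and SAP gives a time for the imaging follow-up in four places outside the analysis text, and all four say 6 months.

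- **Statement of the tertiary aim:** the arms are to be compared on "signal changes in chronic SIJ dysfunction with PRP vs. SAI therapy at 6 months".
- **Tertiary/Exploratory Aim, Design, treatment effect:** the sub-study looks for "changes in cartilage or periarticular signal with PRP and SAI therapy between baseline and 6 months".
- **Tertiary/Exploratory Aim, Design, joint comparison:** differences between the painful and the pain-free joint in the same patient "will be investigated in both baseline and 6 months studies".
- **Advanced MR Imaging Parameters:** "MRI will be obtained pre-procedure as a baseline", "then again 6 months after SAI or PRP to measure T1 and T2 maps".

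The Analyses paragraph at the end of the same aim says something else. The arms are compared on the "mean difference in T1rho relaxation time from baseline to 3 months using a two-sample t-test". It continues: "This method of analysis will also be performed for T2 mapping intensity, as well as IVIM parameters as stated above".

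**The concern.** The Analyses paragraph is the only place where the between-arm imaging test is specified, and its time point has no matching scan. Read literally, the test cannot be run for any imaging endpoint.

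Two things follow. First, any between-arm imaging result at 6 months would depart from the stated analysis, and the team would have to explain that when reporting. Second, the conflict could mislead whoever books the scans. The contacts listed in the Procedural protocol end at 3 months, when an in-person visit already exists, and the 6-month scan stands outside that list. A scan booked to match the analysis text would miss the time point of the aim, and with 5 patients per arm even one or two such scans would matter.

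**Working it through.** The plan gives no calculated figure on this point. The check is a comparison of the imaging time points, followed by a count.

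**Time points side by side**

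| Place in the protocol | What is fixed there | Time points |
|---|---|---|
| Statement of the tertiary aim | Between-arm MRI comparison | 6 months |
| Tertiary aim, Design | Change with PRP and SAI | Baseline, 6 months |
| Tertiary aim, Design | Painful versus pain-free joint | Baseline, 6 months |
| Advanced MR Imaging Parameters | Scan acquisition | Baseline, 6 months |
| Tertiary aim, Analyses | Between-arm test of change | Baseline, **3 months** |
| Tertiary aim, Analyses | Paired test between joints | None given |

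**Is there a 3-month scan elsewhere?** The Procedural protocol says what happens at that visit: a blinded nurse will "perform in-person functional and disability assessments and obtain NRS and opiate measures at 1 and 3 months post-procedure". MRI is not among these items. The three amendments do not mention MRI or its timing, so the mismatch is not left over from a change they describe.

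**Does the hypothesis settle it?** No. It gives 3 months for pain and disability, then mentions MRI-quantified changes without a time of their own.

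**How many comparisons are affected?** The Outcomes paragraph of the tertiary aim lists one T1rho measure, one T2 measure and four IVIM parameters (f, D*, fD*, D). The method sentence covers all of them: 1 + 1 + 4 = 6 between-arm comparisons.

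**How many patients have data?** The sub-study plans 5 + 5 = 10 patients.

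- At 3 months, the time in the analysis text: 0 of 10 are scheduled for a scan.
- At 6 months, the time in the schedule: 10 of 10 are scheduled, before any drop-out.

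**Where might the wording come from?** The analysis paragraphs of the primary and secondary aims use nearly the same sentence, with a change to 3 months and a two-sample t-test. There it is correct, because NRS, disability and function are measured at 3 months. Carried-over text is the likely explanation, but the documents do not say so.

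**The case against.** The strongest reply is that this is a slip of wording with little consequence. Only one post-treatment scan is planned, and the aim, design and schedule all prespecify 6 months. There is no second time point to choose from, so an analyst who used the 6-month scan would be following the stated aim. A charge of post-hoc selection would be weak. Scans would be booked from the imaging paragraph, which is explicit, so mis-scheduling is conjecture. The count of 0 of 10 describes the sentence, not a loss of information. The sub-study is exploratory, with 5 patients per arm and no power basis.

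Much of this stands. The selection argument is weak and should not carry the point. Mis-scheduling is possible, but nothing in the documents shows it to be likely. The paired comparison of joints is unaffected: the Analyses paragraph gives it no time point, and the Design paragraph places it at baseline and 6 months.

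What does not stand is the inference that the text can be left alone. The error is in the operative analysis statement, not in background. A reader can guess the intended time, but a guess is not a prespecified analysis, and the only sentence that specifies this test contradicts the aim it serves.

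**Conclusion.** The concern holds. As written, all six between-arm imaging comparisons call for a 3-month MRI that the plan does not schedule, so none of them can be run at the stated time. Four statements in the plan say 6 months and one says 3.

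The size is limited. The data needed for the aim are planned, no information or power is lost, and the primary and secondary analyses do not change. The correction should be made, but it does not threaten the trial's main conclusions.

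The conclusion assumes that the imaging paragraph lists every planned scan. Part of the background on imaging was not available to check. It precedes the design sections and is unlikely to contain a scan schedule.

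**What to change.** In the Analyses paragraph of the Tertiary/Exploratory Aim, make the between-arm comparison the change from baseline to 6 months, and state that this applies to T1rho, T2 and each IVIM parameter. The paragraph then agrees with the aim, the design and the scan schedule.

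In the same edit, it would help to state that the paired comparison of painful and pain-free joints is made at baseline and at 6 months, as the Design paragraph already says.

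Record the correction, with its date, before any imaging data are examined, so that the time point is visibly prespecified. The cost is a short wording change, with no additional scans, visits or patients.
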